#### **7.1.1.1. Discontinuation of Study Treatment Prior to Week 16**

Patients who discontinue prior to Week 16 will complete the ETV and the Post-Treatment Follow-Up Period (Period 4). In addition, patients will complete several additional assessments, as detailed in the Schedule of Activities ([Appendix 2](#)).

#### **7.1.2. Discontinuation of Inadvertently Enrolled Patients**

The criteria for enrollment must be followed explicitly. If the sponsor or investigator identifies a patient who did not meet enrollment criteria and was inadvertently enrolled, a discussion must occur between the sponsor clinical research physician/clinical research scientist and the investigator to determine if the patient may continue in the study. If both agree, it is medically appropriate to continue, the investigator must obtain documented approval from the sponsor clinical research physician/clinical research scientist to allow the inadvertently enrolled patient to continue in the study with or without treatment with investigational product.

#### **7.1.3. Permanent Discontinuation from the Study**

Some possible reasons that may lead to permanent discontinuation include:

- Enrollment in any other clinical trial involving an investigational product or enrollment in any other type of medical research judged not to be scientifically or medically compatible with this study
- Participation in the study needs to be stopped for medical, safety, regulatory, or other reasons consistent with applicable laws, regulations, and GCP
- Patient decision: The patient requests to be withdrawn from the study.

Patients who discontinue the study early will have end-of-study procedures performed as shown in the Schedule of Activities ([Appendix 2](#)).

#### **7.1.4. Patients Lost to Follow-Up**

A patient will be considered lost to follow-up if he or she repeatedly fails to return for scheduled visits and is unable to be contacted by the study site. Site personnel are expected to make

diligent attempts to contact patients who fail to return for a scheduled visit or were otherwise unable to be followed up by the site.

## 8. Study Assessments and Procedures

[Appendix 2](#) lists the Schedule of Activities, with the study procedures and their timing (including tolerance limits for timing).

[Appendix 3](#) lists the laboratory tests that will be performed for this study.

Unless otherwise stated in the subsections below, all samples collected for specified laboratory tests will be destroyed within 60 days of receipt of confirmed test results. Certain samples may be retained for a longer period, if necessary, to comply with applicable laws, regulations, or laboratory certification standards.

### 8.1. Efficacy Assessments

Below are brief descriptions of key aspects of the scales used in the study. Complete assessments are included in site training materials.

The following ASAS domains are used to determine ASAS20, ASAS40, ASAS partial remission, and ASAS 5/6 (Sieper et al. 2009, ASAS Handbook):

- 1) Patient Global (Section [8.1.2.2](#))
- 2) Spinal Pain (Section [8.1.2.3](#))
- 3) Function (Section [8.1.2.5](#))
- 4) Inflammation (mean of BASDAI questions 5 and 6) (Section [8.1.2.4](#))
- 5) CRP (Section [8.1.2.19.1](#)) and
- 6) Spinal mobility (lateral spinal flexion) (Section [8.1.2.6](#)).

#### 8.1.1. Primary Efficacy Assessments: ASAS40

The ASAS40 (Anderson et al. 2001; Brandt et al. 2004; Sieper et al. 2009) is derived from patient-reported assessments. An ASAS40 response is defined as a  $\geq 40\%$  improvement and an absolute improvement from baseline of  $\geq 2$  units (range 0 to 10) in  $\geq 3$  of 4 domains (Patient Global, Spinal Pain, Function, and Inflammation) without any worsening in the remaining domain.

#### 8.1.2. Secondary Efficacy Assessments

##### 8.1.2.1. ASAS20, ASAS Individual Components, ASAS Partial Remission, and ASAS 5/6

The ASAS20, ASAS individual components, ASAS partial remission, and ASAS 5/6 responses (Davis et al. 2003; Sieper et al. 2009) are secondary efficacy assessments that are calculated as improvements in respective response rates in multiple disease domains.

Complete definitions of each assessment are provided below.

##### 8.1.2.1.1. ASAS20

The ASAS20 is derived from patient-reported assessments. An ASAS20 response is defined as a  $\geq 20\%$  improvement and an absolute improvement from baseline of  $\geq 1$  units (range 0 to 10) in

$\geq 3$  of 4 domains (Patient Global, Spinal Pain, Function, and Inflammation), and no worsening of  $\geq 20\%$  and  $\geq 1$  unit (range 0 to 10) in the remaining domain.

#### **8.1.2.1.2. ASAS Partial Remission**

The ASAS partial remission is derived from patient-reported assessments. An ASAS partial remission response is defined as a value not above 2 units (range 0 to 10, NRS) in each of the following 4 domains: Patient Global, Spinal Pain, Function, and Inflammation.

#### **8.1.2.1.3. ASAS 5/6**

The ASAS 5/6 includes assessment of all 6 individual ASAS domains listed in Section 8.1 and represents improvement of  $\geq 20\%$  in at least 5 domains.

#### **8.1.2.2. Patient Global (Assessment of Disease Activity)**

From the ASAS Handbook (Sieper et al. 2009), the patient is asked to respond to the following question: “How active was your spondylitis on average during the last week?” The answer is recorded on an NRS and is rated between “0” (not active) and “10” (very active).

#### **8.1.2.3. Spinal Pain**

From the ASAS Handbook (Sieper et al. 2009), the patient is asked to respond to the following 2 questions (on average during the last week):

1. “How much pain of your spine due to ankylosing spondylitis do you have?”
2. “How much pain of your spine due to ankylosing spondylitis do you have at night?”

The answers are recorded on an NRS and are each rated between “0” (no pain) and “10” (most severe pain). The first question is used to derive responses (that is, ASAS40, ASAS20, and so on).

#### **8.1.2.4. Bath Ankylosing Spondylitis Disease Activity Index**

The BASDAI is a patient-reported assessment consisting of 6 questions that relate to 5 major symptoms relevant to rad-axSpA (Garrett et al. 1994; Sieper et al. 2009): 1) Fatigue, 2) Spinal pain, 3) Peripheral arthritis, 4) Enthesitis, 5) Intensity, and 6) Duration of morning stiffness. Patients need to score each item with a score from 0 to 10 (NRS).

BASDAI50 represents an improvement of  $\geq 50\%$  of the BASDAI score from baseline.

#### **8.1.2.5. Bath Ankylosing Spondylitis Functional Index**

The BASFI is a patient-reported assessment that establishes a patient’s functional baseline and subsequent response to treatment (Calin et al. 1995). To complete the BASFI, a patient is asked to rate the difficulty associated with 10 individual basic functional activities. Patients respond to each question using an NRS scale (range 0 to 10) with a higher score indicating worse function.

The patient’s final BASFI score is the mean of the 10 item scores completed on an NRS.

#### **8.1.2.6. Bath Ankylosing Spondylitis Metrology Index—Spinal Mobility**

The BASMI is a combined index comprising the following 5 clinical measurements of spinal mobility in patients with rad-axSpA (Jenkinson et al. 1994):

- Lateral spinal flexion
- Tragus-to-wall distance
- Lumbar flexion (modified Schrober)
- Maximal intermalleolar distance
- Cervical rotation.

The BASMI includes these 5 measurements that are each scaled to a score of 0 to 10 depending on the result of the assessment (BASMI linear function). The average score of the 5 assessments gives the BASMI linear result (van der Heijde et al. 2008; Sieper et al. 2009).

The BASMI must be assessed by a rheumatologist or health care provider who meets the qualifications for study assessment.

#### **8.1.2.7. Chest Expansion**

While patients have their hands resting on or behind the head, the assessor will measure the chest's encircled length by centimeter at the fourth intercostal level anteriorly. The difference between maximal inspiration and expiration in centimeters will be recorded. Two tries will be recorded. The better measurement (larger difference) of 2 tries (in centimeters) will be used for analyses.

The measurement of chest expansion must be assessed by a rheumatologist or health care provider who meets the qualifications for study assessment.

#### **8.1.2.8. Occiput to Wall Distance**

The patient is to make a maximum effort to touch the head against the wall when standing with heels and back against the wall (occiput). Then the distance from occiput to wall is measured. Two tries will be recorded. The better (smaller) measurement of 2 tries (in centimeters) will be used for analyses.

The measurement of occiput to wall distance must be assessed by a rheumatologist or health care provider who meets the qualifications for study assessment.

#### **8.1.2.9. Ankylosing Spondylitis Disease Activity Score**

The ASDAS is a composite index to assess disease activity in AS (Machado et al. 2011a, 2011b; Zochling 2011). The parameters used for the ASDAS (with CRP as acute phase reactant) are the following:

- 1) Total back pain (BASDAI question 2)
- 2) Patient global (Section [8.1.2.2](#))
- 3) Peripheral pain/swelling (BASDAI question 3)
- 4) Duration of morning stiffness (BASDAI question 6)
- 5) CRP in mg/L.

The  $ASDAS_{crp}$  is calculated with the following equation:  $0.121 \times \text{total back pain} + 0.110 \times \text{patient global} + 0.073 \times \text{peripheral pain/swelling} + 0.058 \times \text{duration of morning stiffness} + 0.579 \times \text{Ln}(\text{CRP}+1)$  (Machado et al. 2015). (Note: CRP is in mg/liter, the range of other variables is from 0 to 10; Ln represents the natural logarithm.)

Four disease activity states have been defined by ASAS consensus (Machado et al. 2011c):

- ASDAS <1.3 defines inactive disease
- $1.3 \leq \text{ASDAS} < 2.1$  defines moderate disease activity
- $2.1 \leq \text{ASDAS} \leq 3.5$  defines high disease activity
- ASDAS > 3.5 defines very high disease activity.

Clinically important improvement is defined as change  $\geq 1.1$  units, and major improvement is defined as change  $\geq 2.0$  units (Machado et al. 2011b).

#### **8.1.2.10. Maastricht Ankylosing Spondylitis Enthesitis Score**

The MASES is an index used to measure the severity of enthesitis (Heuft-Dorenbosch et al. 2003). The MASES assesses 13 sites for enthesitis using a score of “0” for no activity or “1” for activity. Sites assessed include costochondral 1 (right/left), costochondral 7 (right/left), spinal iliaca anterior superior (right/left), crista iliaca (right/left), spina iliaca posterior (right/left), processus spinosus L5, and Achilles tendon proximal insertion (right/left). The MASES is the sum of all site scores (range 0 to 13); higher scores indicate more severe enthesitis.

The MASES must be assessed by a rheumatologist or health care provider who meets the qualifications for study assessments.

#### **8.1.2.11. Spondyloarthritis Research Consortium of Canada–Enthesitis Score**

The SPARCC enthesitis is an index used to measure the severity of enthesitis (Maksymowych et al. 2009). The SPARCC assesses 16 sites for enthesitis using a score of “0” for no activity or “1” for activity. Sites assessed include Medial epicondyle (left/right [L/R]), Lateral epicondyle (L/R), Supraspinatus insertion into greater tuberosity of humerus (L/R), Greater trochanter (L/R), Quadriceps insertion into superior border of patella (L/R), Patellar ligament insertion into inferior pole of patella or tibial tubercle (L/R), Achilles tendon insertion into calcaneum (L/R), and Plantar fascia insertion into calcaneum (L/R). The SPARCC is the sum of all site scores (range 0 to 16). Higher scores indicate more severe enthesitis.

The SPARCC must be assessed by a rheumatologist or health care provider who meets the qualifications for study assessments.

#### **8.1.2.12. Peripheral Arthritis**

##### **8.1.2.12.1. Tender Joint Count**

The number of tender and painful joints will be determined by examination of 46 joints (23 joints on each side of the patient’s body). The 46 joints to be assessed and classified as tender or not tender are detailed in site training materials. Any joints that require intra-articular injections during the study (according to Section 6.8) are to be excluded from evaluation from the time of the injection to the conclusion of the study.

Joint assessments must be assessed by a rheumatologist or health care provider who meets the qualifications for study assessments. To minimize interobserver variation, particularly during the Blinded Treatment Dosing Period (Period 2), it is recommended that the same assessor performs the TJC for a given patient. Missing, replaced, ankylosed, or arthrodesed joints will be

identified by the investigator at the screening visit (Visit 1) and will be excluded from evaluation during the study.

The TJC data will be collected electronically.

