### **Corticosteroids:**

#### Blinded Treatment Dosing Period (Period 2):

*Oral corticosteroids:* If on oral corticosteroids, the dose must not exceed 10 mg/day of prednisone or its equivalent and must be stable for at least 4 weeks prior to baseline randomization. During Period 2, treatment alterations in oral corticosteroid dose are strongly discouraged.

*Parenteral corticosteroids (IV, intramuscular, intra-articular):* Treatment with any parenteral corticosteroids is not permitted within 6 weeks prior to baseline or during Period 2.

*Inhaled and topical steroids:* Regular use of inhaled or topical steroids will be permitted during any study period.

Extended Treatment and Post-Treatment Follow-Up Periods (Periods 3 and 4):

*Oral corticosteroids:* As of Week 16, adjustments of oral corticosteroids are allowed; however, the maximum dose is not to exceed 10 mg/day of prednisone or its equivalent at any time during these periods.

*Parenteral corticosteroids (IV, intramuscular, intra-articular):* As of Week 16, intra-articular injection of corticosteroid may be allowed, as needed. The joint injected must be designated along with the medication in the eCRF and must be recorded as unevaluable on the TJC/SJC assessment.

*Inhaled and topical steroids:* Regular use of inhaled or topical steroids will be permitted during any study period.

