		SPARCC enthesitis score = 0	SPARCC enthesitis score = 0 refers to complete resolution in enthesitis Analysis of SPARCC enthesitis score = 0 only applies to patients with baseline enthesitis (SPARCC enthesitis >0).	Missing if >20% (ie, 4 or more) sites are missing. If ≤20% missing, then imputed sum = sum of scores from nonmissing sites x 16/ no. of nonmissing sites.

Description and Derivation of Primary and Secondary Efficacy Outcomes

Tender Joint Count (TJC)	The number of tender and painful joints will be determined by examination of 46 joints (23 joints on each side of the patient’s body). The 46 joints are assessed and classified as tender or not tender.	TJC total score	Adjusted sum of the pain/tenderness for all 46 joints: $\left(\frac{\text{sum of all joints checked to be painful/tender}}{\text{number of evaluable joints}}\right) \times 46$ See Appendix 4 for details.	Missing if baseline or observed value is missing
		Proportion of patients with TJC = 0 when baseline TJC > 0	TJC > 0 refers to incidence of TJC. Analysis of TJC = 0 only applies to patients whose baseline TJC > 0.	Missing if observed value is missing
		Proportion of patients with TJC = 0 for patients with current or historical peripheral arthritis at baseline	TJC > 0 refers to incidence of TJC. Analysis of TJC = 0 only applies to patients with current or historical peripheral arthritis at baseline.	If more than half of the joint scores are non-evaluable, the total score will be missing.
		TJC change from baseline	Calculated as: observed TJC – baseline TJC only applies to patients whose baseline TJC > 0.	Missing if observed value is missing
Swollen Joint Count (SJC)	The number of swollen joints will be determined by examination of 44 joints (22 joints on each side of the patient’s body). The 44 joints are assessed and classified as swollen or not swollen.	SJC total score	Adjusted sum of the pain/tenderness for all 44 joints: $\left(\frac{\text{sum of all joints checked to be swollen}}{\text{number of evaluable joints}}\right) \times 44$ See Appendix 4 for details.	Missing if observed value is missing

Description and Derivation of Primary and Secondary Efficacy Outcomes

		Proportion of patients with SJC = 0 for patients with current or historical peripheral arthritis at baseline	SJC > 0 refers to incidence of SJC. Analysis of SJC = 0 only applies to patients with current or historical peripheral arthritis at baseline.	Missing if baseline or observed value is missing

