Measure	Variable	Analysis Method (Sections 6.1, 6.3)	Population (Section 6.1.5)	Comparison/Time Point	Analysis Type
		Descriptive statistics of MASES = 0 (or SPARCC=0)	Extended Treatment Period Population with Baseline MASES >0 (or SPARCC >0)	No treatment group comparisons during Period 3	Other secondary efficacy analyses (Section 6.10.4)
Peripheral Arthritis	TJC and SJC change from baseline	MMRM	ITT Population with Baseline TJC>0 (or SJC>0)	IXE80Q2W & IXE80Q4W vs. placebo at Week 16 and all other postbaseline visits in Period 2	Other secondary efficacy analyses (Section 6.10.4)
		ANCOVA with mBOCF	ITT Population with Baseline TJC>0 (or SJC>0)	IXE80Q2W & IXE80Q4W vs. placebo at Week 16 and all other postbaseline visits in Period 2	Other secondary efficacy analyses (Section 6.10.4)
		Descriptive statistics of change from baseline	Extended Treatment Period Population	No treatment group comparisons during Period 3	Other secondary efficacy analyses (Section 6.10.4)
	TJC = 0, SJC=0, respectively, when patients had current or historical peripheral arthritis at baseline	Logistic regression analysis with NRI; Fisher’s exact test with NRI	ITT Population with current or historical peripheral arthritis at baseline	IXE80Q2W & IXE80Q4W vs. placebo at Week 16 and all other postbaseline visits in Period 2	Other secondary efficacy analyses (Section 6.10.4)
		Descriptive statistics of TJC = 0 (or SJC =0)	Extended Treatment Period Population with current or	No treatment group comparisons during Period 3	Other secondary efficacy analyses (Section 6.10.4)

Measure	Variable	Analysis Method (Sections 6.1, 6.3)	Population (Section 6.1.5)	Comparison/Time Point	Analysis Type
			historical peripheral arthritis at baseline		
	TJC = 0 when baseline TJC >0 (similarly SJC = 0 when baseline SJC >0)	Logistic regression analysis with NRI; Fisher's exact test with NRI	ITT Population with Baseline TJC>0 (or SJC>0)	IXE80Q2W & IXE80Q4W vs. placebo at Week 16 and all other postbaseline visits in Period 2	Other secondary efficacy analyses (Section 6.10.4)
		Descriptive statistics of TJC = 0 (or SJC =0)	Extended Treatment Period Population with Baseline TJC>0 (or SJC>0)	No treatment group comparisons during Period 3	Other secondary efficacy analyses (Section 6.10.4)

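### In the Period 3 joint summaries, a steroid-injected joint leaves both parts of the TJC/SJC ratio, so injecting a baseline-active joint scores as improvement and injecting the only active joint scores as TJC=0 or SJC=0

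*Protocol*

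**What the plan says.** Protocol Section 6.8 (Corticosteroids) bars parenteral steroid before Week 16: "Treatment with any parenteral corticosteroids is not permitted within 6 weeks prior to baseline or during Period 2". It then opens the route for Periods 3 and 4: "As of Week 16, intra-articular injection of corticosteroid may be allowed, as needed". The injected joint is named in the eCRF and "must be recorded as unevaluable on the TJC/SJC assessment". Sections 8.1.2.12.1 (TJC) and 8.1.2.12.2 (SJC) carry the same rule: "Any joints that require intra-articular injections during the study (according to Section 6.8) are to be excluded from evaluation". They make the removal permanent: such joints "are to be excluded from evaluation from the time of the injection to the conclusion of the study".

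SAP Table RHBW.6.4 defines the TJC total as an "Adjusted sum of the pain/tenderness for all 46 joints". The numerator is the "sum of all joints checked to be painful/tender", the denominator is the number of evaluable joints, and the ratio is multiplied by 46. SJC has the same form with 44. The table sets a total to missing only when over half the joints cannot be assessed, and it refers to Appendix 4 for details. Appendix 4 is redacted in the public SAP.

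Table RHBW.6.5 summarises change in TJC/SJC and the TJC=0 and SJC=0 proportions in Period 3 descriptively, without group comparisons. Protocol Section 3 and SAP Section 4 place these data under the objective of showing that the effect is maintained to Week 52. The Schedule of Activities puts the Period 3 joint counts at Weeks 24, 36 and 52, and at early termination.

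**The concern.** Rescaling by the number of evaluable joints is a sound adjustment when a joint is unassessable for reasons unrelated to its state, such as a joint replaced before the trial. It treats the absent joint as if it resembled the patient's other joints. An injected joint is different: the protocol describes it as one that required injection, so the joint's own condition prompts its removal. An active joint is dropped, and the remaining joints stand in for it.

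Nothing visible in the SAP corrects for this. A few injections do not trigger the missing-score rule. Nonresponder imputation (Sections 6.3.1 and 6.10.1) treats unmet criteria, missing data and treatment discontinuation as failure, but it does not mention a joint injection. A patient whose last active joint was treated with local steroid can therefore enter the Week 52 summary as having complete joint resolution on ixekizumab. At stake is the accuracy of the descriptive joint evidence on maintenance of effect.

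**Working it through.** The plan gives no figure for injected joints, so there is none to reproduce. The check applies the visible SAP formula.

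**Inputs.** Total joints T = 46 (TJC) or 44 (SJC), from Protocol 8.1.2.12 and SAP Table RHBW.6.4. Active joints are k and evaluable joints are E. All joints are assumed evaluable at baseline (E = T).

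**Formula.** Score = T × k/E. After one active joint is injected and excluded, score = T × (k − 1)/(E − 1).

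**Direction.** k/E − (k − 1)/(E − 1) = (E − k)/[E(E − 1)], which is positive whenever k < E. Removing an active joint therefore lowers the score unless every evaluable joint is active.

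**Case 1: one baseline-active joint injected, all others unchanged.**

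| Baseline count | TJC after (change) | SJC after (change) |
|---|---|---|
| 1 | 46 × 0/45 = 0 (−1.00) | 44 × 0/43 = 0 (−1.00) |
| 2 | 46 × 1/45 = 1.02 (−0.98) | 44 × 1/43 = 1.02 (−0.98) |
| 3 | 46 × 2/45 = 2.04 (−0.96) | 44 × 2/43 = 2.05 (−0.95) |
| 5 | 46 × 4/45 = 4.09 (−0.91) | 44 × 4/43 = 4.09 (−0.91) |
| 10 | 46 × 9/45 = 9.20 (−0.80) | 44 × 9/43 = 9.21 (−0.79) |

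If the injected joint were kept as active, every change in this table would be 0. The first row is scored as complete resolution. The score is also 0 if all active joints are injected, for example 2 of 2: 46 × 0/44 = 0.

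**Case 2: the injected joint became active after baseline.** Baseline TJC 3, now 4, and the new joint is injected: 46 × 3/45 = 3.07. The change is scored as +0.07 instead of +1. The worsening is hidden, but no improvement is recorded.

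**Case 3: the injected joint was not counted as active** (for example swollen but not tender, when scoring TJC). A TJC of 3 becomes 46 × 3/45 = 3.07, slightly worse.

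**Do the missing-data rules catch it?** The total goes missing only above 23 of 46 or 22 of 44 non-evaluable joints. One or a few injections do not reach that, so the score is observed and nonresponder imputation is not triggered.

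**Possible size at group level.** The documents give no injection rate, so this is an assumed range. Let r be the true TJC=0 rate and f the fraction of true non-resolvers whose last active joint is injected. The reported rate is r + (1 − r)f.

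- r = 30%: f = 2% gives 0.30 + 0.70 × 0.02 = 31.4%; f = 10% gives 37.0%.
- r = 50%: f = 2% gives 0.50 + 0.50 × 0.02 = 51.0%; f = 10% gives 55.0%.

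**The case against.** The strongest objection is that Appendix 4, the joint-count algorithm, is redacted, and a rule for injected joints would naturally sit there. That stands: the point rests on the visible formula and must be confirmed against the appendix before anything is changed.

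Second, exclusion is a deliberate rule, applied consistently in three protocol sections, and it avoids crediting ixekizumab with a steroid effect. If one of three swollen joints settles after injection, scoring it as observed gives SJC 2, while exclusion gives 2.05. This is fair, and it is why scoring the joint as observed is not proposed. It does not help when the only active joint is injected, because exclusion then gives 0, the same score as if the steroid had worked completely.

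Third, the reach is narrow: Period 3 is descriptive, all patients are then on ixekizumab, and joint counts enter neither the primary nor any major secondary outcome. This also stands and limits the weight of the point.

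Fourth, carrying forward the joint's last-visit status would be a poor remedy. A joint quiet at Week 36 that flares and is injected before Week 52 would be carried forward as quiet. That is correct, and the fix below avoids it.

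A reader might also infer that the rule always favours ixekizumab, or that a patient whose only active joint is injected is SJC=0 at every later visit. The documents support neither. Cases 2 and 3 above are exceptions to the first, and the second fails once any remaining joint becomes active. Nor do they support reading each injection as proven treatment failure, since Section 6.8 allows injections simply as needed.

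**Conclusion.** The point holds on the visible scoring rule, with low to moderate weight. Excluding one injected, baseline-active joint lowers the scored count by about 0.8 to 1.0 at baseline counts of 1 to 10, if other joints are unchanged and all were evaluable at baseline. If it was the only active joint, the patient is scored as resolved while no other joint is active.

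The effect is confined to the Period 3 TJC/SJC summaries. A reader might infer that the placebo-controlled results are biased as well. They are not under the permitted rules: Week 16 joint comparisons could be touched only by an injection in Period 2, which would be a protocol deviation, and ASAS40 and the major secondary outcomes do not use joint counts.

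How far the Week 52 rates move cannot be determined, because the number of injected patients is not given. The conclusion also assumes that Appendix 4 contains no rule that already deals with injected joints.

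**What to change.** First confirm what Appendix 4 says about injected joints. If it has no such rule, then in the SAP:

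- In the Period 3 TJC=0 and SJC=0 summaries, count a patient as not resolved at visits after an intra-articular injection, at minimum as a sensitivity summary beside the current one. This follows the logic of Sections 6.3.1 and 6.10.1, where a patient who cannot stay on treatment is a failure because benefit is not sustained.
- For change from baseline in TJC/SJC, add a sensitivity summary that keeps the injected joint in the denominator and scores it as active from the injection date, without carrying forward its last-visit status.
- Report the number of patients injected in each treatment group.

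Joints excluded at screening stay excluded. These are scoring rules only; nothing changes about when injections may be given.

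The cost is SAP wording and a link to the eCRF record that already names the injected joint. Week 52 joint rates would become slightly less favourable. The sensitivity rule is conservative for joints that later settle, which is why it should be shown beside the current summary and labelled as such.
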